### 10.1.3 Sensitivity Analyses of Primary Endpoint(s)

A sensitivity analysis will be conducted with regard to the primary endpoint. The analysis will be identical to the one identified above, except that the Per Protocol Analysis Set is used. In this analysis, subjects will be assigned to the treatment actually received. In the event of a decrease in dose (from 16 mg/kg to 8 mg/kg) the subject will be assigned to the highest dose treatment received. This analysis will exclude data following major protocol deviations and other factors which may influence the primary outcome. Major protocol deviations will be determined without knowledge of treatment assignment (i.e., prior to unblinding). [Appendix 16.7](#) provides a list of major protocol deviations and other reasons for exclusion from the Per Protocol Analysis Set.

The second (to be conducted for Per Protocol Analysis Set) sensitivity analysis is a tipping point analysis that will employ multiple imputation for missing data (missing change from baseline in ACR) using multiple regression to provide multiple complete data sets [[Buuren 2018](#)]. The same MMRM model will be used to analyze the imputed complete data sets (missing ACR values will be imputed for planned ACR assessments up to the individual subjects last performed visit before EOS and EOS visit). If the original analysis indicates a significant effect, the tipping point analysis adds a value, delta, to the imputation model to assess the sensitivity of the “missing at random” assumption. In this case, the delta is

increased (decreased) until statistical significance is lost. A conclusion of the sensitivity analysis is based on whether the value of delta at the time significance is lost is interpreted as likely given the data observed.

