10.3.2 Efficacy Analyses

Primary Endpoint

The primary analysis is a mixed effects model, repeated measures (MMRM) analysis of the change from Baseline through 24 weeks of log ACR, with the primary treatment comparison at Week 16 (Visit 10). The model will include treatment (at 3 levels: 8 mg/kg CSL346, 16 mg/kg CSL346, and placebo), Baseline log ACR, the stratification variable related to the concomitant use of SGLT2 inhibitors, visit (as a categorical factor), and interactions between visit and each of the other model terms as factors. The primary comparison of interest is a contrast of 0.5 (8 mg/kg CSL346 + 16 mg/kg CSL346) – Placebo. Estimated treatment effect of individual CSL346 dose levels versus placebo will also be summarized. The treatment comparisons will be expressed as a percent difference in treatments, calculated as $100\% \times (\text{geometric mean ratio of the treatment comparison} - 1)$. For the purposes of this analysis, Baseline will be defined as the geometric mean of the 6 values obtained before treatment (3 values from Visit 3 and 3 values immediately before treatment at Visit 4). The procedure for determining the covariance model for log ACR residuals will be defined in the SAP. There will be only 1 primary comparison so there is no consideration of adjustment for multiple comparisons. Comparisons of CSL346 dose levels with placebo will be considered exploratory. The primary analysis will be performed using the ITT Analysis Set.

Two sensitivity analyses will be considered for the primary endpoint. The first such analysis considers the effects of COVID-19 on the primary endpoint. For subjects with treatment discontinuation / interruption due to logistical pandemic-related reasons, observations greater than 28 days after last on-schedule SC infusion received will be excluded. For subjects who received no infusions due to logistical pandemic-related reasons, all data will be excluded. For subjects who contract COVID-19 infection during the study, observations on or after the infection date will be excluded. If both conditions apply, then data exclusion will begin at (a) 28 days after the last SC infusion or (b) the infection date, whichever is earlier. The second sensitivity analysis is a tipping point analysis that will employ multiple imputation for missing data using multiple regression to provide multiple complete data sets. The same MMRM model will be used to analyze the complete data set.

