### **10.1 Analysis of Primary Endpoint(s)**

#### **10.1.1 Primary Estimand**

The primary interest is to quantify the treatment effect of CSL346 under the situation where SGLT2i may be a possible effect modifier and is included in the model. The estimand for the ITT Analysis Set is the average effect of CSL346 on the geometric mean ACR at 16 weeks averaged across subjects receiving and not receiving SGLT2i. All data collected through Week 24 will be used in the analysis.

The primary estimand in line with the primary interest of the study is described as follows:

- Treatment Condition: four SC administrations of CSL346 or placebo over a 12-week period (Day 1, Weeks 4, 8 and 12) where the primary comparison is between CSL346 at Week 16, regardless of dose, and placebo, while subjects have not died. The “treatment policy strategy” will be used, i.e. changes in dose, for example from 16 mg/kg to 8 mg/kg OR the number of subcutaneous injections, or treatment discontinuation/non-initiation, or other miscellaneous factors influencing ACR will not be taken into account in the primary analysis;
- Population: the target patient population defined by T2DM and DKD and further eligibility criteria;

- Variable: change from baseline at 16 weeks of log ACR;
- Population-level summary: difference in treatments, calculated as  $100\% \times (\text{geometric mean ratio of the treatment comparison} - 1)$  based on log ACR.

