#### **10.4 Missing Data and Imputation**

To avoid missing data with regard to the primary endpoint, ACR, procedures will be in place to maximize the ability to collect first morning voids for every subject at every planned visit. Likewise, every attempt will be made to retain subjects in the study once they are randomized. Therefore, it is anticipated that missing data with regard to the primary endpoint will be kept to a minimum. Imputation is only being considered for the sensitivity analysis for the primary endpoint.

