#### SAS code for multiple imputation

```
Proc mi data=data_set out=data_set_imputed nimpute=10
seed=xxxx round=0.01;
  Var treatment visit sglti_yn patient chglnacr;
  Monotone reg(chglnacr = treatment visit sglti_yn patient);
run;
```

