## 16.7 Factors to be Addressed in Per Protocol Analysis Set

The following define major events which could result in subjects' data being removed from the per protocol analysis set. Subjects' data may be removed completely or from the time of the major event up to the end of subject's study participation.

At a specific time point, ACR measurements are to be used in summaries and analysis as long as there are at least 2 FMVs for that time point (4 FMVs for baseline) available.

- Extrinsic factors with the potential to impact ACR during treatment period. For any such occurrences, data points at or beyond the date of the occurrence will be excluded from analysis. [These data will be provided by CSL.]
  - Protocol deviations:
    - Subjects with substantial change in blood pressure medications or DKD medications;
    - Prohibited concomitant medications;
    - Initiation of lipid lowering agent;
    - Change in SGLT2i doses;
    - Change in dose in agents that impact tubular secretion of serum creatinine (fibrates).
    - Missed intermittent dose
  - Cardiac AESI with heart failure.
- Study drug [to be derived by Parexel]:
  - For subjects receiving fewer than 4 doses of the investigational product, all data on or after the date of the last dose + 4 weeks + 1 day will be excluded. If no dose is administered then all data for that subject will be excluded.
- Violation of study entry criteria. In these cases, all data from these subjects will be excluded from analysis. [These data will be provided by CSL.]
  - Baseline Glycosylated HbA1c  $\geq 12\%$ ;
  - Change in SCr from Visit 1 (<63 Days before Day 1) to Visit 2 (Day -21)  $> 0.3$  mg/dL (26.5  $\mu\text{mol/L}$ );
  - Uncontrolled hypertension: SBP  $> 160$  mmHg or DBP  $> 100$  mmHg prestudy (SBP $>150$  mmHg at randomization).

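### The tipping-point analysis does not stress-test the ITT Week 16 result: wrong analysis set, contradictory imputation window, and an imputation model blind to baseline and to the subject's own visits

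*SAP*

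**What the plan says.** The primary analysis uses the ITT set (SAP 10.1.2). Its estimand follows a treatment-policy strategy: "treatment discontinuation/non-initiation, or other miscellaneous factors influencing ACR will not be taken into account in the primary analysis" (SAP 10.1.1).

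SAP 10.1.3 then gives two sensitivity analyses. The first repeats the MMRM on the Per-Protocol set. Of the other it says: "The second (to be conducted for Per Protocol Analysis Set) sensitivity analysis is a tipping point analysis". On how the gaps are filled it says "The same MMRM model will be used to analyze the imputed complete data sets", and adds in parentheses: "missing ACR values will be imputed for planned ACR assessments up to the individual subjects last performed visit before EOS and EOS visit".

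The imputation step in SAP 16.1 is a PROC MI call with the line "Monotone reg(chglnacr = treatment visit sglti_yn patient".

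SAP 16.7 lists what the Per-Protocol set removes. For subjects with fewer than four doses, "all data on or after the date of the last dose + 4 weeks + 1 day will be excluded". Data also go after medication changes, prohibited medication, a missed dose or a cardiac AESI with heart failure, and some entry violations remove the whole subject.

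SAP 10.4 confirms that nothing else is imputed: "Imputation is only being considered for the sensitivity analysis for the primary endpoint". In the protocol (10.3.2) the tipping point is one of the checks on the primary endpoint: "Two sensitivity analyses will be considered for the primary endpoint". No Per-Protocol restriction appears there, and SAP section 5 does not list one among its changes from the protocol.

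**The concern.** A tipping-point analysis asks how bad the unseen values would have to be before the conclusion fails. It answers that only if it works on the data set behind the conclusion, shifts the values that are truly unseen at the primary visit, and starts (delta = 0) from a credible missing-at-random fit. The SAP falls short on each count.

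- **Set.** The claim is ITT. The check is run on data from which observed ACR has been removed.
- **Window.** Taken at its word, the parenthetical fills gaps up to the last attended visit, plus EOS. A subject who leaves after Week 8 and misses Visit 10 gets no Week 12 or Week 16 value, so the data set is not complete at the primary visit. The printed code has no cut-off, so two programmers could deliver different analyses.
- **Model.** The code runs on one row per visit with no CLASS statement, so patient number enters as a numeric slope. Baseline log ACR, treatment-by-visit and the subject's other ACR values are absent, although the MMRM code in the same appendix uses baseline, both interactions and an unstructured covariance. The code has no delta step, and the text does not say which arm receives delta.

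The first two can combine badly. A subject who stops dosing but attends Visit 10 has a known Week 16 value replaced and shifted, while a subject who truly misses Visit 10 has none imputed.

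At stake is the robustness statement reported beside the primary result, not the result itself.

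**Working it through.** **1. Scale, from the plan's own figures (SAP 4.4).** Inputs: SD 0.65, effect ln(0.73) = -0.315, one-sided alpha 0.10, 94 evaluable (47 per arm).
- The normal approximation gives 46 per arm (92). The t-test gives power 84.8% at 46 and 85.4% at 47, so 94 reproduces.
- Critical effect: t(0.90; 92 df) x 0.65 x sqrt(2/47) = 0.173, as stated.
- Planned dropout: 94/(1 - 0.06) = 100.
- Ceiling: 1 - 94/124 = 24%. Completers must also have received all doses, so this is an upper bound on Week 16 missingness, not an expected rate.

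If delta is added to imputed CSL346 values and f is the share of that arm imputed at Week 16, then roughly: tipping delta = (|effect| - 0.173)/f. For an effect of -0.315 this is 2.37 at f = 6%, 1.18 at 12% and 0.59 at 24%. For -0.20 it is 0.45, 0.23 and 0.11.

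**2. Analysis set.** Last dose at Week 8 is Day 57. Exclusion starts at Day 57 + 28 + 1 = Day 86. Collected Week 16 (Day 113) and EOS (Day 169) values are therefore removed from the Per-Protocol data. No size was simulated for this part.

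**3. Window, strict reading.** If EOS is imputed and Week 16 is not, delta reaches Week 16 only through the MMRM covariance. Under an assumed exchangeable correlation rho and k other visits filled, the regression weight of Week 16 on EOS is rho/(1 + (k - 1)rho). For a subject leaving after Week 8 (Weeks 2, 4, 8 and EOS, k = 4):
- rho = 0.6: 0.6/2.8 = 0.21
- rho = 0.8: 0.8/3.4 = 0.24

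So about a quarter of delta arrives. Simulation (8 scenarios of 200 trials, unstructured model) agrees: delta = +1.0 moved the Week 16 contrast by 0.009 instead of 0.036 at 6% missing, and by about 0.04 to 0.05 instead of 0.18 at 24%. The ratio was 3.5 to 4.8.

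**4. Printed model, every missing row imputed.** Simulation: 28 scenarios of 400 trials, 10 imputations, 25/25/50 subjects, SD 0.65, Week 16 effect -0.315. Assumed:
- exchangeable correlation 0.6 or 0.8, baseline unrelated to change;
- numeric coding of arm, visit and patient;
- dropout either random or with log-odds slope 1.5 per SD of the previous ACR change.

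The comparator is one-row-per-subject imputation. Monte Carlo SE of the difference is at most 0.004.

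| Dropout | Week 16 effect, printed | Week 16 effect, comparator | Tipping delta, printed | Tipping delta, comparator |
|---|---|---|---|---|
| 6%, random | -0.30 to -0.31 | -0.31 | | |
| 6%, ACR-driven, both arms | -0.29 to -0.30 | -0.31 | | |
| 24%, ACR-driven, both arms | -0.24 to -0.26 | -0.32 | 0.44-0.52 | 0.70-0.86 |
| 6% of all subjects, CSL346 only | -0.36 to -0.39 | -0.31 | 1.60-1.82 | 1.23-1.32 |
| 12% of all subjects, CSL346 only | -0.40 to -0.45 | about -0.32 | 0.98-1.16 | 0.60-0.68 |

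The formula in step 1 agrees with the last row. With f = 12/50 = 0.24, (0.315 - 0.173)/0.24 = 0.59 for the comparator. The printed model gives (0.40 - 0.173)/0.24 = 0.95 to (0.45 - 0.173)/0.24 = 1.15.

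The cause is that imputed Week 16 correlates -0.01 to 0.06 with the subject's own Week 4 value, against 0.45 to 0.80 under the comparator. A leaver with high ACR is filled in near the arm average.

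A second simulation used a harsher mechanism: 50 per arm, correlation 0.4 to 0.8, the CSL346 subjects with the highest Week 8 values leaving, and random dropout on placebo. The printed model gave -0.34 to -0.37 at 6% and -0.40 to -0.49 at 24%. Sequential regression on baseline and earlier visits gave -0.31 to -0.32.

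**The case against.** **Excluded is not the same as missing.** SAP 8.1 defines missing data as fields left blank, and collected values removed under 16.7 are not blank. It is fair that no sentence says they will be imputed. But building complete data sets on the Per-Protocol set means filling those gaps. If they are not filled, the data sets are not complete. Values truly missing under ITT do remain missing for subjects kept in the Per-Protocol set, so they are partly examined, though not on the ITT data.

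**Window and model are largely alternatives.** Under the strict window, the Week 16 imputation biases mostly do not arise; under the code as printed there is no window problem. This stands, and the two sets of figures must not be added. Whichever reading is taken, one fault applies. Few subjects may be affected, since the protocol seeks Visit 10 and EOS after withdrawal (4.3.2).

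**The code is a template.** It has placeholders, and SAP section 3 puts implementation details in a separate document. If patient were declared a CLASS effect, imputed Week 16 would correlate 0.55 to 0.83 with Week 4. Bias at 6% dropout would be at most 0.034, and 12% CSL346-only dropout would attenuate the effect (-0.25 to -0.29 against about -0.32). So the size, and there the sign, depends on the numeric reading. But that rescue needs a statement the SAP does not print, while the MMRM code beside it does print one. Baseline would still be absent.

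**Small at the planned rate.** With 6% dropout in both arms the bias is about 0.01 to 0.03, under a quarter of the design SE, 0.65 x sqrt(2/47) = 0.134. With 6% CSL346-only dropout, deltas of 1.23-1.32 and 1.60-1.82 mean roughly 3.4- to 3.7-fold and 5- to 6-fold ACR increases, which is robust either way. This stands.

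**Conclusion.** The concern holds: the analysis is wrong as written. The Per-Protocol assignment, the clash between the window and complete data sets, and the missing predictors are all in the SAP text and need no simulation. The Per-Protocol restriction is also an undeclared departure from the protocol.

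The sizes rest on assumptions, because the documents give neither a dropout mechanism nor visit correlations. At the planned 6% with balanced dropout and an effect near -0.315, the harm is small. It becomes material if dropout is uneven between arms, if it approaches the 24% ceiling, or if the observed effect lies near -0.173. The printed model can then understate robustness (tipping delta 0.44-0.52 instead of 0.70-0.86) or overstate it (0.98-1.16 instead of 0.60-0.68). The strict window would separately cut delta's reach to about a quarter.

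The primary estimate and test do not change. This should be fixed, but it does not threaten the trial's main analysis.

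**What to change.** - Run the tipping point on the ITT set with all collected ACR. A Per-Protocol version may stay as an extra; if so, say whether excluded values are imputed.
- State that every missing planned visit through Week 24, including Week 16 after dropout, is imputed, and delete the conflicting parenthetical.
- Replace the PROC MI step with a one-row-per-subject imputation: treatment and SGLT2i use as class variables, baseline log ACR and earlier visits as predictors, and a first step for intermittent gaps. Drop patient as a predictor.
- Prespecify that delta is added to imputed CSL346 values, with its direction and grid.
- If any Per-Protocol restriction remains, list it in SAP section 5.

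The cost is SAP wording and a short block of code. It uses data already collected and leaves the primary analysis as it is.

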#### **10.1.4 Subgroup Analyses of Primary Endpoint(s)**

Two a priori subgroup analyses to be considered will be based on the strata defined by the presence or absence of concomitant use of a SGLT2i and by eGFR status at baseline (20 - <45, 45 - <60, 60 - <90,  $\geq 90$  mL/min/1.73m^2). Each subgroup will be analyzed in a similar manner as the primary analysis as a mixed effects model, repeated measures (MMRM) analysis of the change from baseline through 24 weeks of log ACR, with the primary treatment comparison at Week 16 (Visit 10). The model will include treatment, baseline log ACR, and interactions between visit and each of the other model terms as factors. For subgroup analysis by SGLT2i, the factor of SGLT2i is not to be included in the model. Scatterplots of ACR and/or change in ACR by eGFR will also be provided.

### **10.2 Analysis of Key Secondary Endpoint(s)**

Blood pressure, serum creatinine and eGFR calculated using the Chronic Kidney Disease Epidemiology Collaboration (CKD-EPI) formula [[Levey et al. 2009](#)], [Section 8.2.7](#), will employ a model similar to the primary endpoint. These endpoints will not be log-transformed prior to analysis. The analysis for these continuous endpoints is an MMRM analysis of change from baseline to each post-baseline measurement. The model will include treatment, stratification related to the concomitant use of SGLT2is, visit (as a categorical factor), and interactions between visit and each of the other model terms, as well as the corresponding baseline measurement as a covariate (refer to [Section 16.1](#) for respective SAS code). Hypotheses testing will be identical to that of the primary endpoint. Line graphs of the mean response over time will be provided as well as by ACR status.

All of these analyses will be performed on the ITT Analysis Set.

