An overview of identified and potential risks and planned risk mitigation in this phase 2a study is provided in Table 1.

Table 1 Risks and Risk Mitigation

Risk	Potential/ Identified	Source	Risk Mitigation
Injection site reactions	Identified	CSL346_1001 data on file	
 Assessment at study visits Guidance for managing local intolerance
Hypersensitivity / anaphylaxis and infusion reactions; antibody formation	Potential	Class effect of humanized proteins	
 Standard measures Measurement of baseline, mid-, and end of study anti-CSL346 antibody
Weight gain	Potential	Knock-out mouse model [Hagberg et al, 2010]	
 Monitor at study visits
Congenital disorders	Potential	Knock-out mouse model [Bellomo et al, 2000] Preclinical study in quails [Tomanek et al, 2006]	
 Inclusion / exclusion criteria Contraception requirements Pregnancy testing Nonclinical studies in later phases
Renal: acute reversible effect on GFR and / or chronic kidney injury	Potential	Theoretical risk due to VEGF-A modulation [Kamarzarian et al, 2018; Izzedine et al, 2010]	
 Inclusion / exclusion criteria Staged approach for enrollment of subjects with moderate renal impairment Frequent monitoring in first 4 weeks of treatment Measure SCr and evaluate albuminuria at each visit Guidance for managing increases in SCr and albuminuria

Risk	Potential/Identified	Source	Risk Mitigation
Cardiac: myocardial dysfunction with chronic dosing	Potential	Knock-out mouse model [Bellomo et al, 2000] Streptozotocin model [Lal et al, 2017] Theoretical risk due to VEGF-A modulation [Touyz et al, 2018]	
 Exclusion criteria, including baseline assessment of LVEF by ECHO Treatment with SOC Baseline and periodic ECG, BNP, and troponin levels Guidance for managing increases in troponin levels
Increased BP	Potential	Theoretical risk due to VEGF-A modulation [Touyz et al, 2018]	
 Exclusion criteria BP measurement Guidance for managing increases in BP

BP = blood pressure; BNP = b-type natriuretic peptide; ECG = electrocardiogram; ECHO = echocardiogram; GFR = glomerular filtration rate; LVEF = left ventricular ejection fraction; SCr = serum creatinine; SOC = standard of care; VEGF = vascular endothelial growth factor.

2 Study Objectives and Endpoints

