#### 4.1.5 Primary Study Hypotheses

The primary study hypothesis is that the ACR geometric mean ratio for CSL346 (8 mg/kg and 16 mg/kg combined) versus placebo (80% CI) at 16 weeks is less than 1. The test for superiority will be conducted at the one-sided, 0.10 alpha level.

Hypotheses will be tested using a one-sided test at  $\alpha=0.10$ :

$$H_0: GMR \geq 1.0 \text{ vs. } H_1: GMR < 1.0$$

$$\left( \text{i.e. } GMR = \frac{0.5 * \left( \text{CSL346}_{\frac{8\text{mg}}{\text{kg}}} + \text{CSL346}_{\frac{16\text{mg}}{\text{kg}}} \right)}{\text{Placebo}} \right),$$

where GMR is the geometric mean ratio of the change from baseline in albumin/creatinine ratio.

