#### 4.1.6 Key Secondary Study Hypotheses

The key secondary hypothesis regarding decreases in serum creatinine, blood pressure (SBP and DBP) and eGFR will be conducted in a similar manner as for the primary study hypothesis, but using mean instead of geometric mean.

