### 16.9 Directionality of One-sided Tests

Since treatment comparisons in this study are based on one-sided tests, we need to designate the direction of these tests. Directionality and method for calculating one-sided p-value from the two-sided p-value is specified in the table below.

Parameter Name	Better (Lower or Higher)	Comment	One sided p-value calculated as:
Biomarkers of Lipid Metabolism: Total Cholesterol	Lower	Compared to PBO	estimate < 1 p-one sided=p/2 estimate >= 1 p-one sided=1-p/2
Biomarkers of Lipid Metabolism: Triglycerides –	Lower	Decreased triglycerides in the fed state, compared to PBO could indicate activity, but in fasted samples, no change would be predicted.	estimate < 1 p-one sided=p/2 estimate >= 1 p-one sided=1-p/2
Biomarkers of Lipid Metabolism: HDL –	Higher	Compared to PBO	estimate < 1 p-one sided=1-p/2 estimate >= 1 p-one sided=p/2
Biomarkers of Lipid Metabolism: LDL –	Lower	Compared to PBO	estimate < 1 p-one sided=p/2 estimate >= 1 p-one sided=1-p/2
Biomarkers of Lipid Metabolism: (Fasting) Glycerol –	Higher	Smaller (or no) increase in fasting glycerol, NEFA, ketones compared to PBO could indicate activity	estimate < 1 p-one sided=1-p/2 estimate >= 1 p-one sided=p/2
Biomarkers of Lipid Metabolism: (Fasting) NEFA –	Higher		estimate < 1 p-one sided=1-p/2 estimate >= 1 p-one sided=p/2
Biomarkers of Lipid Metabolism: (Fasting) Ketones –	Higher		estimate < 1 p-one sided=1-p/2 estimate >= 1 p-one sided=p/2
Biomarkers of VEGF Family: Urinary VEGF-A	Lower	Decrease in total VEGF-A compared to PBO could indicate activity	estimate < 0 p-one sided=p/2 estimate >= 0 p-one sided=1-p/2
Biomarkers of VEGF Family: Urinary Soluble VEGF-R1	Lower	Decrease in total VEGF-R1 compared to PBO could indicate activity	estimate < 0 p-one sided=p/2 estimate >= 0 p-one sided=1-p/2
Biomarkers of Tubular Injury: KIM-1	Lower	Compared to PBO	estimate < 0 p-one sided=p/2 estimate >= 0 p-one sided=1-p/2

Biomarkers of Tubular Injury: NGAL	Lower	Compared to PBO	estimate < 0 p-one sided=p/2 estimate >= 0 p-one sided=1-p/2
Biomarkers of Tubular Injury: MCP-1	Lower	Compared to PBO	estimate < 0 p-one sided=p/2 estimate >= 0 p-one sided=1-p/2
Biomarkers of Tubular Injury - EGF	Higher	Compared to PBO	estimate < 0 p-one sided=1-p/2 estimate >= 0 p-one sided=p/2
Biomarkers of Tubular Injury: Clusterin	Lower	Compared to PBO	estimate < 0 p-one sided=p/2 estimate >= 0 p-one sided=1-p/2

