Circulating Biomarker of Inflammation: sTNFR1	Lower	Compared to PBO	estimate < 0 p-one sided=p/2 estimate >= 0 p-one sided=1-p/2
ACR	Lower	Compared to PBO	estimate < 1 p-one sided=p/2 estimate >= 1 p-one sided=1-p/2
eGFR	Higher	Compared to PBO	estimate < 0 p-one sided=1-p/2 estimate >= 0 p-one sided=p/2
Serum Creatinine	Lower	Compared to PBO	estimate < 0 p-one sided=p/2 estimate >= 0 p-one sided=1-p/2
Blood pressure	Lower	Compared to PBO	estimate < 0 p-one sided=p/2 estimate >= 0 p-one sided=1-p/2
Weight	Lower	Compared to PBO	estimate < 0 p-one sided=p/2 estimate >= 0 p-one sided=1-p/2
HbA1C	Lower	Compared to PBO	estimate < 0 p-one sided=p/2 estimate >= 0 p-one sided=1-p/2
Fasting glucose	Lower	Compared to PBO	estimate < 0 p-one sided=p/2 estimate >= 0 p-one sided=1-p/2

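### SCr, eGFR and blood pressure are tested only for benefit, so a harmful shift in the mean is reported with p of at least 0.5; the SAP also gives eGFR two opposite directions

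*SAP*

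**What the plan says.** **The test**
- SAP 10.2 (blood pressure, SCr, eGFR): "Hypotheses testing will be identical to that of the primary endpoint".
- SAP 4.1.5 defines that primary test: "The test for superiority will be conducted at the one-sided, 0.10 alpha level".
- SAP 16.9 opens: "Since treatment comparisons in this study are based on one-sided tests, we need to designate the direction of these tests". For SCr and blood pressure, where lower is better, its rule is "estimate < 0 p-one sided=p/2 estimate >= 0 p-one sided=1-p/2". For eGFR, where higher is better, it is "estimate < 0 p-one sided=1-p/2 estimate >= 0 p-one sided=p/2".
- SAP 4.1.6 words the hypothesis differently: "The key secondary hypothesis regarding decreases in serum creatinine, blood pressure (SBP and DBP) and eGFR will be conducted in a similar manner".

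**The role of these endpoints in the protocol**
- Table 1 (Section 1.4) lists as a potential risk "Renal: acute reversible effect on GFR and / or chronic kidney injury". It also lists increased BP, with the mitigation "Guidance for managing increases in BP".
- Sections 9.1.3.2 and 9.1.3.4 make SCr and BP increases AESIs. Sections 3.7.1 and 3.7.2 name them in the stopping criteria.
- Section 2.2.1 words the objectives neutrally, as evaluating the effect on SCr, eGFR and BP.
- Section 10.3.3 places the repeated-measures models for SCr, eGFR and BP under Safety Analyses, on the Safety Analysis Set, with no sidedness stated.

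SAP 10.2 runs the same models under Efficacy Analyses on the ITT Analysis Set. SAP Section 5, which lists changes from the protocol, does not mention this.

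**The concern.** For the primary endpoint a one-sided test makes sense, because the question is whether ACR falls. For SCr, eGFR and BP the protocol's concern is at least as much about movement in the harmful direction. Protocol Table 12 even provides for confirmed SCr rises of 0.3 to under 0.7 mg/dL that the investigator judges to be expected from the product's activity.

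Under 16.9, the larger the observed harm, the closer the reported p-value comes to 1. A reader scanning a results table would take p = 0.98 for SBP as no effect, when it marks a difference that is nominally significant in the wrong direction. The model contrast is the only planned adjusted between-group comparison of these means. AESI and threshold tables pick up individual extremes and can miss a modest shift in the average.

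**Working it through.** **1. Confirm which test is carried over.** The inputs are from SAP 4.4: SD 0.65, effect ln(0.73) = -0.315, 94 evaluable subjects. Allocation is 1:1:2, so pooled CSL346 against placebo is 47 against 47.
- n per group = 2 × [0.65 × (1.2816 + 1.0364) / 0.3147]² = 45.8, so 46 per group or 92 in total, against the stated 94.
- SE = 0.65 × √(2/47) = 0.134. Power = Φ(0.3147/0.134 - 1.2816) = 0.857 (0.854 by noncentral t), against the stated 85%.
- Critical difference with 92 df = 0.173, as stated.

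The plan's figures reproduce with one-sided alpha 0.10, so that is the test 10.2 passes to SCr, eGFR and BP.

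**2. Apply the 16.9 rule to a harmful estimate.** Reported p = 1 - p/2, where p is two-sided. This needs no SD. Since p cannot exceed 1, the reported value is never below 0.5.

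| Two-sided p (harm side) | Reported one-sided p |
|---|---|
| 0.20 | 0.90 |
| 0.05 | 0.975 |
| 0.01 | 0.995 |
| 0.001 | 0.9995 |

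**3. Put this in clinical units.** The documents give no SD for these endpoints, so the SDs and shifts below are assumptions, shown as ranges. z = shift / (SD × √(2/47)), normal approximation, 47 per group.

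| Assumed harm | Assumed SD | z | Two-sided p | Reported p |
|---|---|---|---|---|
| SBP +5 mmHg | 10 | 2.42 | 0.015 | 0.992 |
| SBP +5 mmHg | 12 | 2.02 | 0.043 | 0.978 |
| SBP +5 mmHg | 15 | 1.62 | 0.106 | 0.947 |
| SBP +5 mmHg | 18 | 1.35 | 0.178 | 0.911 |
| SCr +0.1 mg/dL | 0.15 to 0.4 | 3.23 to 1.21 | 0.001 to 0.23 | 0.9994 to 0.887 |
| eGFR -5 mL/min/1.73m² | 7 to 15 | 3.46 to 1.62 | 0.0005 to 0.106 | 0.9997 to 0.947 |

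**4. What the planned interval shows.** SAP 10.2 refers to the 16.1 code, whose ESTIMATE statements request two-sided 80% limits. For SBP +5 with SD 12, SE = 12 × √(2/47) = 2.475, and the 80% CI is 5 ± 1.2816 × 2.475, about 1.8 to 8.2 mmHg. It lies wholly on the harm side.

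**5. Sensitivity to harm.** Take a harm the mirror size of the primary effect, 0.3147/0.65 = 0.484 SD. Then z = 0.484 × √(47/2) = 2.35.
- Reported p at the expected estimate: Φ(2.35) = 0.990 (two-sided 0.019).
- Chance that the benefit-only test rejects: Φ(-1.2816 - 2.35) = 0.0001.
- Chance that the 80% CI lies above zero harm: Φ(2.35 - 1.2816) = 0.86.
- Chance that a two-sided 0.05 test detects the harm: Φ(2.35 - 1.960) = 0.65.

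**6. eGFR direction.** SAP 4.1.6 frames the hypothesis as a decrease in eGFR, and 10.2 read literally (same as primary) also tests for a lower value. On that reading a fall would earn a small p and count as success. Appendix 16.9 makes higher better, so the same fall earns 1-p/2. The SAP modification history shows that 16.9 was added in Final 3.0 to set directions. It is the more specific rule and is the one used above, but the two sections cannot both stand.

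**The case against.** A reader might infer that the plan cannot flag harm on these endpoints, or that it conceals it. The documents do not support that.
- The 80% intervals show direction and size for each dose and for the pooled contrast.
- SCr and BP increases are AESIs with numerical definitions and are tabulated (SAP 11.2).
- Both have potential-clinical-importance limits (SAP Tables 3 and 4). By-visit values and changes are summarised on the Safety Analysis Set, and creatinine also has shift tables (SAP 11.3, 11.4.2).
- The declared summary measure is mean (SD), which shows either direction.
- The unblinded IDMC has stopping criteria that name SCr and BP increases.
- The 16.9 rule is reversible: a reported 0.978 converts back to two-sided 2 × (1 - 0.978) = 0.044, or 0.043 before rounding.

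All of this stands. It makes the problem one of labelling in the model-based test. eGFR is the least covered, since it has no AESI or threshold of its own, although it is calculated from SCr.

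It is also fair that this is a phase 2a study with no power claim for these endpoints, and that replacing the 80% CI with a 95% CI would make the interval less sensitive to harm (step 5: 0.86 against 0.65). The second point argues for adding the 95% CI and keeping the 80% one. The first does not justify a benefit-only direction: SAP 10.1.2 cites early development to support one-sided 0.10 for the primary test, and no such reason is given for parameters the protocol treats as safety measures.

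**Conclusion.** The point holds as a reporting fault in the test of SCr, eGFR and BP. Under 16.9 any harmful mean difference is reported with p between 0.5 and 1. How near 1 depends on size: about 0.89 for a harm of 0.25 SD and 0.99 for 0.484 SD, with 47 per group. For a 5 mmHg SBP rise it is 0.992 to 0.911 over an assumed SD of 10 to 18 mmHg. The rule itself rests on no assumption; the clinical examples rest on the assumed SDs and a normal approximation. Harm would remain visible in other planned outputs, so the test mislabels it and does not hide it.

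Two inconsistencies need correcting with it: the opposite eGFR directions in SAP 4.1.6 and 16.9, and the unlisted move from the Safety Analysis Set to ITT. The change should be made; nothing here touches the primary conclusion.

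**What to change.** - **SAP 10.2:** replace the sentence on hypothesis testing with the treatment difference, a two-sided p-value and a two-sided 95% CI for SCr, eGFR, SBP and DBP. Keep the 80% CI already produced.
- **SAP 16.9:** remove the rows for these endpoints and exempt them from the opening sentence. Deleting the rows alone would leave 4.1.6, 10.2 and that sentence prescribing one-sided tests with no direction defined.
- **SAP 4.1.6:** reword as a two-sided comparison, which also removes the conflict over eGFR.
- **SAP 16.1:** add 95% limits to the estimates for these endpoints.
- **Analysis set:** use the Safety Analysis Set as in protocol 10.3.3, or list and justify the change in SAP Section 5.

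The cost is SAP wording and small code edits. A nominal benefit on these unpowered endpoints would need a somewhat stronger result. The primary test, sample size and data collection do not change.
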